Rationale: The use of antipsychotic medication is increasing worldwide (1-3). It is well established that patients with a severe mental illness and patients treated with atypical antipsychotics have excess metabolic dysfunction (4) and are at an increased risk of cardiovascular disease (4, 5). Currently, monitoring of usage and effects of antipsychotic treatment (5-7), as well as cardiovascular risk screening in patients with severe mental illness or antipsychotic treatment (6) is not sufficient. General practitioners experience barriers regarding knowledge, collaboration with psychiatrists, and patient compliance (6). To overcome these barriers, the primary care cooperative Onze Huisartsen Arnhem BV developed in close collaboration with Radboudumc a transmural collaborative care model for cardiovascular risk management and medication review for patients using atypical antipsychotics in general practice (TACTIC). We have recently explored the feasibility of TACTIC in a pilot study (CMO 2020-7240) and used our findings to optimize the intervention for assessment of its effectiveness.

Objective: To assess the effectiveness of TACTIC regarding predicted cardiovascular risk and mental quality of life. The secondary objective is to assess its cost-effectiveness.

Study design: Incomplete cluster randomised stepped wedge trial.

Study population: Adult patients (>25yrs) from general practices, using atypical antipsychotics prescribed by their general practitioner.

Intervention: TACTIC is a one-time transmural intervention comprising three steps: 1) online information video to inform patients about the cardiovascular risks of antipsychotic use and about the procedures of the multidisciplinary meeting, 2) a multidisciplinary meeting with the patient to review his or her antipsychotic use and cardiovascular risk and to provide tailored treatment advice, and 3) a follow-up contact with the general practitioner to translate the treatment advice into an individualised action plan through shared decision making. TACTIC complements the current regular cardiovascular risk management programme for primary prevention of cardiovascular diseases of the primary care cooperative Onze Huisartsen BV that has been based on the specific guidelines of Dutch College of General Practitioners (NHG) and has been used in the Arnhem region since several years

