Main study parameters/endpoints: Change in cardiovascular risk, as measured with the QRISK3 score, and change in mental quality of life, as measured with the MHI5 questionnaire.

Nature and extent of the burden and risks associated with participation, benefit and group relatedness:*Burden and risk associated with the intervention:*

Patients who are eligible and who want to participate in the study will be included in the regular cardiovascular risk management programme of the Arnhem primary care cooperative. This programme includes, according to current Dutch guidelines, 1 to 5 consultations with the GP and/or the practice nurse in which physical examination, i.e. measuring blood pressure and body weight, and blood and urine sample collection will take place. The frequency depends on the severity of the cardiovascular risk and the corresponding follow-up period. On top of the regular cardiovascular care patients who participate in the study will also receive the three-step TACTIC intervention. This is a one-time intervention. Patients who are eligible but who do not want to participate in the study will be included in the regular cardiovascular risk management programme, but will not receive the TACTIC intervention.

There is a potential risk associated with participation, as patients whose antipsychotic medication is altered during participation may destabilize mentally. However, this risk is expected to be low. Changes in medication will only take place after this advice has been given in *Step 2* (i.e. multidisciplinary meeting including the patient's GP, a psychiatrist, and the patient self) and has been followed in *Step 3* (i.e. shared decision making between the patient and his/her GP). The advice to change medication will only be given in *Step 2* as the psychiatrist, the GP, and the patient consider this option to be safe. Besides, the advice will only be followed in *Step 3* if both patient and GP feel safe with it. In addition, TACTIC contains precautionary measures to prevent destabilisation, i.e. any change in antipsychotic medication is accompanied with the advice of follow up consultations with the general practitioner or mental health nurse, and all patients who alter their antipsychotic medication will have a crisis prevention plan to ensure safety.

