1. OBJECTIVES

Primary objective: to assess the effectiveness of TACTIC in patients using atypical antipsychotics in general practice on cardiovascular risk and mental quality of life.

Secondary objectives: to assess cost effectiveness of the intervention TACTIC and its effectiveness regarding individual risk factors for cardiovascular disease.

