3.4 Sample size calculation

The sample size calculation is based on the following findings and expectations. Our pilot showed a reduction of the mean QRISK3 score of 1.9 points. This was after a follow-up period of 3 months, and under suboptimal intervention conditions, e.g. unclear expectation management, modified information meeting due to the corona pandemic. The standard deviation of the difference of QRISK3 score was 3.4 and the standard deviation of a single measurement was 12. This means there is a high reliability on patient level.

$$r_s = 1 - \frac{(SD_{diff}/SD)^2}{2} \approx 0.95$$

We expect that in the trial, after optimisation of the TACTIC procedures, we will be able to detect a reduction of a clinically relevant mean QRISK3 score of 2.5 points in the intervention group, compared to the control condition. Given an SD of 12, an intraclass correlation (ICC) of 0.10, and an α of 0.05, 500 simulated trials indicate that 32 general practices with each 12 patients are needed to provide a power of at least 80%. Given drop-out rates of 20% observed in our pilot study and less than 10% in a UK primary care study evaluating a comparable intervention (15), we include 15 patients per cluster. The required total number of participants will be 480 patients in 32 (or more) clusters.

This calculated sample size has also enough power to detect a clinically relevant improvement of 5 points on de mental health inventory, the mental domain of the SF36, which will be our second primary outcome.

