5. METHODS

5.1 Study parameters/endpoints

5.1.1 Main study parameters

- Our first primary outcome measure is the QRISK3 score (11). The QRISK3 algorithm (www.qrisk.org/three) calculates a person's risk of developing a cardiovascular event (e.g. a heart attack or stroke) over the next 10 years. The score presents the average risk of people with the same risk factors as those entered for that person. The QRISK3 is the preferred algorithm for assessing cardiovascular risk according to the NICE guideline Cardiovascular Disease (18). It includes severe mental illness and use of atypical antipsychotics as predictors for cardiovascular disease, which makes it suitable for use in our study.

The QRISK3 score is calculated based on age, gender, ethnicity, Townsend deprivation score, smoking status, diabetes status, having chronic kidney disease,

atrial fibrillation, migraines, rheumatoid arthritis, systemic lupus erythematosus, severe mental illness or a family history of premature coronary heart disease in a first degree relative, being on blood pressure treatment, on regular steroid tablets, or on atypical antipsychotic medication, having a diagnosis of or treatment for erectile dysfunction, levels of cholesterol/HDL ratio, systolic blood pressure, standard deviation of blood pressure, and Body Mass Index. As the Townsend deprivation score is not applicable to the Dutch population, we will set this to 0, meaning neither deprived nor affluent, as is advised by the authors. The QRISK3 score can range from 0 to 100%. We consider a decrease of 2.5%-points as clinically relevant.

- Our other primary outcome measure is the Mental Health Inventory, five-item version (MHI-5), which is a measure for the mental quality of life (19). The MHI-5 is a derivative of the 36-item short form health survey, the SF36, and assesses symptoms of depression and anxiety, loss of behavioural or emotional control, and psychological well-being in the prior four weeks. The MHI-5 ranges from 0 to 100, where a score of 100 equals perfect mental health. A score of 60 or higher is seen as good mental health, whereas a score below 60 is seen as poor mental health. We will consider an increase of 5 points as clinically relevant.

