The MHI-5 consists of five questions with each six answer categories: continuously-mostly-often-sometimes-rarely-never. The answers of the positively formulated questions (questions 3 and 5) will be assigned the values 5, 4, 3, 2, 1, and 0, respectively. The

answers of the negatively formulated questions (questions 1, 2, and 4) will be assigned the values 0, 1, 2, 3, 4, and 5, respectively. Subsequently, a sum score will be calculated, multiplied by 4, resulting in an MHI-5 score ranging from 0 to 100, where a score of 100 equals perfect mental health.

Data analysis will be performed according to the intention-to-treat principle. Data from patients who discontinued follow-up will be included in the analysis up to the point of dropout. Descriptive analyses will be performed to describe the patient characteristics. Mean and standard deviation (std) or median and interquartile range for continuous characteristics and number and percentages for categorical characteristics will be determined. The relationship between treatment and outcome measures measured at 5, 10, 15, and 20 month follow up will be analysed with mixed three level linear or logistic regression, taking into account that the times of measurement are clustered within patients, and patients within general practices. We will perform a model with a random intercept and all other variables fixed. To test the effect of the intervention a model with time, group (intervention or control) and the interaction between time and group will be performed. A value of $p < 0.05$ will be considered statistically significant for all analyses, based on two-sided testing. Analyses will be performed using the Statistical Package for Social Sciences (SPSS, IBM Corp., Armonk, NY) version 25.

We will present QRISK3 scores and MHI-5 scores as means (SDs) for every measurement point, with notification of the number of patients included in the calculation.

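### Section 7.1 tests two primary outcomes each at an unadjusted two-sided 0.05, and no rule says how the two results decide the single primary effectiveness objective

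*Protocol*

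**What the plan says.** The Protocol states a single primary objective, "to assess the effectiveness of TACTIC in patients using atypical antipsychotics in general practice on cardiovascular risk and mental quality of life" (section 1); the Summary says the same. Two outcomes serve it. Section 5.1.1 opens with "Our first primary outcome measure is the QRISK3 score" and then names MHI-5 as the other primary measure. Section 3.4 says of the mental health inventory, "which will be our second primary outcome".

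On the significance level, section 7.1 states that p below 0.05 "will be considered statistically significant for all analyses, based on two-sided testing". Section 3.4 plans QRISK3 at that same level ("Given an SD of 12, an intraclass correlation (ICC) of 0.10, and an α of 0.05") for at least 80% power. It adds that the resulting sample size is also enough for a 5-point improvement on MHI-5, with no separate alpha and no power figure. No interim analyses are planned (section 6.4), so alpha is not spent elsewhere.

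No section splits alpha, turns the labels first and second into a testing order, or says whether one or both outcomes must show benefit.

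**The concern.** One objective with two tests at full alpha leaves the success rule open until the results are known. If only QRISK3, or only MHI-5, reaches p below 0.05 in the favourable direction, nothing in the protocol prevents that result from being reported as effectiveness. The error rate of the primary claim would then be nearly double that of a single test.

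Direction matters as well. The Summary acknowledges that "patients whose antipsychotic medication is altered during participation may destabilize mentally", although it rates this risk as low. QRISK3 could improve while MHI-5 worsens, and the protocol does not say how such a result would bear on the objective. That is a matter of interpretation and does not change the error rate, but the same rule can settle it.

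**Working it through.** **Inputs.** Two primary outcomes (sections 3.4 and 5.1.1). Two-sided 0.05 per test (section 7.1), hence 0.025 in the direction of benefit. QRISK3 power of at least 80% at alpha 0.05 (section 3.4). Assumed, because the protocol does not give them: one signed treatment contrast per outcome, the correlation between the two test statistics, and the power for MHI-5.

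**The plan's own figure.** 12 / (1 − 0.20) = 15 patients per cluster, and 15 × 32 = 480, as stated. The power simulation cannot be rerun, because the incomplete layout is in a figure that is not shown. An approximate check with 12 per cluster gave 78.4% for a complete cross-sectional stepped wedge and above 99% for a complete cohort with within-patient correlation 0.95. The incomplete layouts tried ranged from about 60% to over 99%. The error rates below do not depend on this.

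**If either outcome suffices and neither has a true effect.**
- Independent tests: 1 − 0.975² = 0.0494, or 4.9%, against 2.5% for one test.
- Correlated tests (bivariate normal, each cut at 1.960): 4.8% at correlation 0.2, 4.5% at 0.5, 3.9% at 0.8.
- Upper bound: 0.025 + 0.025 = 5.0%.

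**If both are required.** The false-claim chance is at most 2.5%, reached when one outcome truly improves and is almost sure to be significant while the other has no effect. If neither has an effect and the tests are independent, it is 0.025² = 0.06%.

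**If each outcome supports only its own claim.** Each claim keeps its 2.5%.

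**Holm for benefit** (critical values 2.241, then 1.960; the second test is opened only by a significant benefit).
- False-benefit chance, independent tests, neither effective: 1 − 0.9875² = 2.48%.
- If a significant worsening could also open the second test, this would be about 2.52% for independent tests and 2.71% at correlation −0.5. Hence the restriction to benefit.
- Power for an outcome with exactly 80% at two-sided 0.05: its expected z is 1.960 + 0.842 = 2.802. At the first Holm cut, power is Φ(2.802 − 2.241) = 0.712. The remaining 0.800 − 0.712 = 0.088 is recovered only when the other outcome passes its own cut.
  - Other outcome null: 0.712 + 0.088 × 0.0125 = 0.713.
  - Other outcome also at 80%, independent: 0.712 + 0.088 × 0.712 = 0.775 (0.765 at correlation 0.5).
- By the same steps, 90% becomes 84% (other null) or 88% (other at 80%), and 95% becomes 91% or 94%.

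**Both-required power.** With 80% for each and independence, 0.80 × 0.80 = 64%.

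**The case against.** The strongest reply is that the inflation needs a rule the protocol does not contain. The objective joins the outcomes with *and*, each has its own relevance threshold (2.5 percentage points and 5 points), and section 3.4 considers power for each separately. That fits a requirement for both, or two outcome-specific conclusions, at least as well as an either-suffices claim. This stands. A reader might infer that the trial as designed has a 4.9% false-benefit rate, or 1 − 0.95² = 9.75% counting both directions. The documents do not support that: 4.9% applies only under the either-suffices reading, and 9.75% would also count worsening as success.

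A second reply is that multiplicity rules commonly belong in the statistical analysis plan. Silence would not be a finding, but section 7.1 is not silent. It fixes an unadjusted threshold for every analysis, and a later alpha split would contradict it.

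A third is that the figures presuppose one directional contrast per outcome. Section 7.1 names a model with time, group and their interaction, and does not say which term is the primary test. If time is categorical, the interaction has several parameters and no single direction. This also stands: the contrast must be named before any rule of this kind can work.

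Finally, Holm would leave section 3.4 out of step with section 7.1 unless both are edited. That is correct and is included in the fix.

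**Conclusion.** The point holds in conditional form. The protocol puts two primary outcomes under one effectiveness objective, tests each at the full two-sided 0.05, and states no rule for combining them. If a benefit on either is taken as success, the false-benefit chance is about 4.9% with independent tests, 4.5% at correlation 0.5 and at most 5.0%, against 2.5%. This rests on one directional contrast per outcome, no true effect on either, and an assumed correlation. The threshold is adequate if both outcomes are required, or if each result is claimed only for itself.

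Two further inferences should be resisted. The labels first and second do not set a hierarchy, because no section uses them that way. Section 3.4 is not wrong about joint power, because it states none. This is a gap in the primary inference that should be closed. It is not a fatal flaw.

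**What to change.** Before data are seen, amend section 7.1 to name one treatment-effect contrast per primary outcome as the primary test. For these two tests, replace the general threshold with one of these rules:

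- **(a)** *QRISK3 and MHI-5 are tested for benefit by the Holm procedure at a family-wise two-sided 5%. The outcome with the stronger evidence of benefit is tested at two-sided 0.025; only if it shows significant benefit is the other tested at two-sided 0.05. Only significant benefit counts towards effectiveness. Any significant worsening of either outcome (two-sided 0.05) is reported alongside.*
- **(b)** *Effectiveness is claimed only if QRISK3 and MHI-5 both show significant benefit, each at two-sided 0.05.*

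Limit the existing 0.05 sentence to all other analyses.

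Make section 3.4 match. Under (a), restate the QRISK3 power for the Holm threshold. Under (b), state that joint power is below either single power.

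The cost is a few sentences and a loss of stated power: under (a), from exactly 80% to about 71–77%, and less if true power is higher. The reliability quoted in section 3.4 suggests that for QRISK3, but the layout needed to confirm it is not shown. No new data or change in patient numbers is proposed.

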7.2 Secondary study parameter(s)

We will convert the EQ-5D index into a utility score, using the Dutch algorithm. The utility score has a maximum of 1, indicating optimal health. A utility score of 0 equals death, but the score can also be negative, as some conditions are thought to be worse than death. By multiplying the utility score with the amount of time in which the score is applicable and then aggregating these scores over the relevant timeframe (trapezium method), we will compute quality-adjusted life years (QALYs) (22).

The Liverpool University Neuroleptic Side Effect Rating Scale (LUNSERS) is self-rating scale for measuring the side-effect of antipsychotic medications. LUNSERS was developed by researchers within the University of Liverpool to indicate the extent of side-effects experienced by patients medicated with neuroleptic drugs. The scale consists of 41 known side effects of neuroleptics. Each 'side-effect' listed is scored on a five point

rating scale of 0 – 4, i.e. 0 = 'Not at all' and 4 = Very much. A total score can be calculated by adding all item scores and then be graded into 'very low', 'low', 'average', 'high', and 'very high', based on the percentiles (16). who have a clinically relevant improvement of at least the minimal clinically important difference (MCID), defined as 0.5 x SD of the baseline mean

7.3 Other study parameters

We will perform a sub analysis on the QRISK3 score, determining the proportion of patients reaching 1) an absolute risk reduction of 2.5%, which we consider as clinically relevant, and 2) a proportional risk reduction of 20% of their optimal achievable reduction. To give an example: a patient has a 10-year cardiovascular risk of 20%, but after perfectly optimising all changeable risk factors, is able to reach a 10-year cardiovascular risk of 10%. When, after the intervention, the patient reaches a QRISK3 score of 17%, this means the patient reached a 3% absolute risk reduction (i.e. 20% - 17%), and a 30% proportional risk reduction (i.e. 3% / (20% - 10%)).

As mentioned in chapter 6.1.1, the Townsend Deprivation Score is not applicable to the Dutch population. We do know, however, that deprivation has impact on cardiovascular risk. Therefore, we want to perform a secondary analysis on the QRISK3 score in which we use the Dutch equivalent of deprivation ("achterstandsindex"). In the Netherlands, we use a deprivation index for patients with low social economic status, based on employment, income and percentage of non-western immigrants. This deprivation index is applicable for approximately 10% of the Dutch population.

We decided to apply the Townsend Deprivation Score at p20 (below which are the 20% most deprived of the British population) for the 10% most deprived patients in our population. By choosing p20 instead of p10, we stay on the safe side and might underestimate the effect of deprivation, but we find this more important than overestimating its impact.

8. ETHICAL CONSIDERATIONS

8.1 Regulation statement

This study will be conducted according to the principles of the Declaration of Helsinki of 2013.

8.2 Recruitment and consent

Recruitment of patients has been described in section 6.3 Study procedures. After being found eligible for participation, the investigator will contact the patient for informed

consent. The patient has the opportunity to ask additional questions before giving consent. If desired, the patient can contact an independent physician, who knows about the study, but is not involved in execution of the study.

The patient information letter and informed consent form can be found attached to this research protocol. Together with the patient information letter for adults, we provide an “easy reading” version for patients with low literacy, which is based on the patient information letter model for children under 16 years of age, provided by the CCMO.

8.3 Objection by minors or incapacitated subjects (if applicable)

Some eligible patients live in supervised communities (for instance RIBW) and are incapacitated. However, patients who are registered in a general practice are usually less incapacitated than those who are for example cared for by an intellectual disability physician. It is important that these patients have the opportunity to participate in this study because, both individually and as a group, they often are at risk of being overtreated with antipsychotic medication and undertreated for cardiovascular risk (24). It is important to study whether TACTIC is suitable for these patients as well. Caregivers and legal representatives will be involved in invitation, the informed consent procedure and during the entire study.

8.4 Benefits and risks assessment, group relatedness

Potential benefit of the intervention

The potential benefit of participation is high, as changes in antipsychotic medication and appropriate cardiovascular risk screening and management will result in decreased cardiovascular risk. The intervention has been developed by the primary care cooperative Onze Huisartsen BV with the intention to implement it in the Arnhem region after demonstrating its feasibility and its (cost-)effectiveness. The intervention is in line with the current guideline of the European Society of Cardiology on cardiovascular disease prevention in clinical practice, which recognises the increased cardiovascular risk for patients with mental disorders (25).

Burden and risk associated with the intervention:

Patients who are eligible and who want to participate in the study will be included in the regular cardiovascular risk management programme of the Arnhem primary care cooperative. This programme includes, according to current Dutch guidelines, 1 to 5 consultations with the GP and/or the practice nurse in which physical examination, i.e. measuring blood pressure and body weight, and blood and urine sample collection will take

place. The frequency depends on the severity of the cardiovascular risk and the corresponding follow-up period. On top of the regular cardiovascular care patients who participate in the study will also receive the three-step TACTIC intervention. This is a one-time intervention. Patients who are eligible but who do not want to participate in the study will be included in the regular cardiovascular risk management programme, but will not receive the TACTIC intervention.

There is a potential risk associated with participation, as patients whose antipsychotic medication is altered during participation may destabilize mentally. However, this risk is expected to be low. Changes in medication will only take place after this advice has been given in *Step 2* (i.e. multidisciplinary meeting including the patient's GP, a psychiatrist, and the patient self) and has been followed in *Step 3* (i.e. shared decision making between the patient and his/her GP). The advice to change medication will only be given in *Step 2* as the psychiatrist, the GP, and the patient consider this option to be safe. Besides, the advice will only be followed in *Step 3* if both patient and GP feel safe with it. In addition, TACTIC contains precautionary measures to prevent destabilisation, i.e. any change in antipsychotic medication is accompanied with the advice of follow up consultations with the general practitioner or mental health nurse, and all patients who alter their antipsychotic medication will have a crisis prevention plan to ensure safety.

Burden and risk associated with outcomes measurements:

Patients fill in questionnaires at baseline and every 5 months during follow-up. Based on our experiences in the pilot study, we expect that it will take approximately 20 minutes to fill in the questionnaire. For the assessment of the primary outcome QRISK3 score routinely collected data from the cardiovascular risk management programme, i.e. blood pressure, body weight, smoking behaviour, and blood cholesterol and glucose levels. At the end of follow-up we will conduct focus-group interviews with a purposive sample of participants to explore experiences with the TACTIC intervention.

